6.3 Point of Enrollment & Enrollment Period

This is an observational study, and the patients will only provide informed consent to allow use of their data. All consented patients are assigned a study identification (ID) number and screened for eligibility in the study. The study will collect data on each patient from (1) the start of the procedure involving External Ventricular Drainage Systems or Accessories until the EVD System is no longer required for drainage and monitoring of CSF, and (2) in patients who have met all eligibility criteria. Patients eligible for the study are identified and informed consent is obtained prior or after the start of treatment with the devices. In case informed consent is obtained:

- Prior to the start of the treatment with the EVD System and Accessories, the data will be prospectively collected from the implantation procedure until the EVD System is no longer required for drainage and monitoring of CSF.
- After the implantation of the EVD System and Accessories and before the EVD System is no longer required for drainage and monitoring of CSF, the data will be retrospectively collected from the implantation procedure until the point of informed consent and prospectively collected until the EVD System is no longer required for drainage and monitoring of CSF.
- After the EVD System is no longer required for drainage and monitoring of CSF, the data will be retrospectively collected from the implantation procedure until the EVD System is no longer required for drainage and monitoring of CSF.

This registry study is anticipated to have an enrollment period of 25 months.

6.4 Comparison of Study Population to Target Population

The registry aims to collect information from patients that represent all ages, demographics, and regions to ensure that the data and conclusions generated from this study are as generalizable as possible while still matching the intended patient population as defined in the Instructions for Use. The patient population of this study will reflect patients who have had a TBI, undergone a major neurosurgical procedure, or some other traumatic, ischemic or hemorrhagic incident requiring EVD.

6.5 Screen Failures and Failures

Participants who are consented to participate in the registry, who do not meet one or more criteria required for participation in the study during the screening procedures, are considered screen failures.

Participants who underwent or undergo a replacement of the Integra or Codman EVD System with an EVD System other than an Integra or Codman EVD System are considered failures and will be discontinued from the date of the Integra or Codman EVD System replacement. The data collected up to the date of the Integra or Codman EVD System replacement will be included as part of the registry study results, as permitted by national laws and regulations.

7 STUDY INTERVENTION/INVESTIGATIONAL PRODUCT

Not applicable – This is a registry; no interventions or investigational products will be used.

8 STUDY ASSESSMENTS AND PROCEDURES

8.1 Informed Consent

Informed consent will occur prior to data collection. **Section 12.1.1.** should be consulted for this process.

8.2 Performance Data to be Collected

Completion of Worksheets/Case Report Forms (CRFs). Sites will transcribe/transmit the information outlined below in study worksheets and CRFs. This information will originate from existing medical and other patient records.

Patient Data:

- Demographics:
 - Gender
 - Year of Birth (YOB)
- Prescribed clinical diagnosis for CSF drainage (e.g., reason the physician prescribed CSF drainage)

Procedural Data:

- Procedural Information CSF drainage:
 - Dates of EVD System and Accessories placement and removal.
 - Details of Catheter and/or EVD System replacement(s), if applicable.
 - Number of initial Catheter Insertion Attempts i.e., number of insertions needed to place Catheter
 - Length of Catheter Tunneling into the Brain i.e., length of tunneling of EVD Catheter in the brain
 - External Ventricular Drainage System and/or accessories used:
 - Brand name
 - Model, SKU, and LOT number(s), if documented

Clinical Performance Data:

- Daily CSF drainage until the EVD System is no longer required for drainage and monitoring of CSF.
- Intracranial access location
- EVD System and Accessories maintenance procedures
- Number, type, and volume of flush(s) used to address occlusions, if applicable.
- Concomitant neuro-interventional and neurosurgical procedures
- Relevant concomitant medications
- Whether the patient required a permanent shunt after the EVD System is no longer required for drainage and monitoring of CSF, if so (name, model)
- In the case of a malfunctioning EVD system and/or Accessories, the component(s) responsible for malfunction or reason for malfunction (where possible)

8.3 Safety and Other Assessments

- Assessment of events related to EVD system and accessories or procedure
 - Medical records will be reviewed for all events that occurred between index procedure and until the EVD System is no longer required for drainage and monitoring of CSF. See

Section 9.1 for complete definitions and information on assessing and documenting events.

- Assessment of noted Device Deficiencies during use of the EVD system and accessories
 - Medical records will be reviewed for device deficiencies (DD) that were documented that occurred between index procedure and until the EVD System is no longer required for drainage and monitoring of CSF. See **Sections 9.1.3 and 9.7.3** for complete definitions and information on assessing and documenting device deficiencies.

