1. PROTOCOL SUMMARY

1.1 Protocol Synopsis

Title:	Post-Market Clinical Follow-Up Registry of the Integra External Ventricular Drainage Systems and Accessories
Short Title:	External Ventricular Drainage PMCF Registry
Protocol number:	C-EXTVDR-001
Study Description:	This post-market follow-up registry will capture clinical data specific to the safety and performance of the Integra External Ventricular Drainage Systems and Accessories.
Background:	
External Ventricular Drainage (EVD) Systems are a temporary system which allow drainage of cerebrospinal fluid (CSF) from the lateral ventricles of the brain. EVD Systems are commonly used within neurosurgery for the management of patients who require drainage of CSF.
 
EVD Systems are regularly used in neurosurgery for diagnostic and therapeutic purposes.
 
Complications of EVD Systems are well recognized, with infection and hemorrhage being the most common ones related to these procedures, followed by ventriculostomy occlusion.
 
The rate of EVD-associated hemorrhage ranges from 18 to 41% in adults as reported in literature, and in pediatric population (single center), it has been found that incidence of hemorrhage at EVD placement to be 10%, and the incidence of hemorrhage on EVD removal to be 21.9%. Studies have demonstrated non patent EVDs in 19-47% of patients.

Pre/Post-Market:	Post-Market Clinical Follow-Up Registry
Study Design:	Observational, multi-center, post-market registry
Primary Objective:	The primary objective of this registry is to capture clinical performance data to confirm the continued performance of the Integra External Ventricular Drainage Systems and Accessories.
Safety Objective:	The safety objective of this registry is to capture clinical safety data to confirm the continued safety of the External Ventricular Drainage Systems and Accessories.
Primary Endpoint:	The primary endpoint is anticipated drainage (i.e., observed drainage consistent with the patient's clinical presentation) of cerebrospinal fluid (CSF) in the clinical setting until the EVD System is no longer required.

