3.6 Safety Endpoints

1. Device- or procedure-related adverse events (AEs) during the use of the device in the patient.
2. Noted Device Deficiencies during use of the device such as malfunction, use errors, or other issues related to the performance or safety of the External Ventricular Drainage Systems and Accessories.

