9.6 Time Period and Frequency for Event Assessment and Follow-Up

As previously described, investigators and/or their staff will review the patient's medical record for events that occurred from device implant until the subject exits the study.

All events will be captured on the appropriate CRF. When possible, signs and symptoms indicating a common underlying pathology should be noted as one comprehensive event (i.e., [possible] influenza instead of chills, fever, and vomiting). The investigator or designee should, to the best of their ability, endeavor to document an outcome/resolution for the event. If no resolution can be found in the medical record, the site will note it as ongoing.

Any medical condition that is present at the time that the subject is screened will be considered as baseline (i.e. medical history and/or conditions) and not reported as an event. However, if the study subject's condition deteriorates at any time during the study, it will be recorded as an event. Any procedures/surgeries should be documented on the Concomitant Neurosurgical and Neuro-interventional Procedures Log from device implant until the until the subject exits the study.

Changes in the severity of an event will be documented to allow an assessment of the duration of the event at each level of severity to be performed. Events characterized as intermittent require documentation of onset and duration of each episode.

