9.7 Event Reporting

All AEs and SAEs information will be collected on all subjects regardless the AE or the SAE is procedure- or device related. AE and SAE recording will start at the point of device implant until the subject exits the study.

Each event must be described as follows in the Electronic Data Capture (EDC) system:

- Event Term: A medically defined diagnosis/symptom. Use the highest level of evidence available.
 - Level 1: Diagnosis
 - Level 2: Symptoms
 - Level 3: Signs
- Event Description: Explain the circumstance of becoming aware of the event, how the subject explained the circumstances surrounding the onset of the event, the underlying cause (the diagnosis), coexisting disease, or other condition or complaint involving the event.
- Event Duration: Document by entering the date of onset (start date) and date of resolution (stop date).
- Event Attribution/Causality: Document causal relationship between event and the investigational product (e.g., causally related, probable, possible, unrelated).
- Event Seriousness: Document as serious or not serious.
- Event Severity: Document as mild (transient and easily tolerated by the subject), moderate (discomfort and interrupts normal activities), or severe (incapacitating with inability to work or do usual activity).
- Treatment: Document as none, medication, hospitalization, surgical, and/or other. Any prescribed medication should be noted in the subject's medical records and transcribed onto the event and Concomitant Medications CRFs. If a surgical or invasive procedure is required for an event, document the procedure on the Procedure Log.
- Outcome: Document as recovered without sequelae, recovered with sequelae, ongoing, death, or other. Events will be followed until a resolution has occurred, until a resolution is no longer expected, the pre-existing condition returns to baseline conditions, or the subject exits the study.

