9.7.3 Reporting of Device Deficiencies (DDs)

The principal investigator shall record every observed DD together with an assessment. All DDs including the analysis of used or explanted investigational devices, where applicable, shall be documented throughout the registry study and managed by the Sponsor.

In this study, review of potential DDs in a patient's medical records will occur from the date of implant to the date of explant.

The Sponsor is responsible for the classification of events and ongoing safety evaluation of the registry study and shall review all DDs. The investigator and Sponsor will determine and document whether the DD could have led to a serious adverse device effect (SADE). In case of disagreement between the Sponsor and the principal investigator(s), the Sponsor shall communicate both opinions to concerned parties described further below in this section.

Every attempt should be made by the Site to save or collect the defective device and packaging, if appropriate, for return to the Sponsor. A qualified company representative will investigate and determine root cause and corrective actions as applicable, and directives will be provided to the site if warranted.

The investigator shall:

- report to the Sponsor, without unjustified delay, all DDs that could have led to a SADE via the supplied CRF (definition in section 9.1).
- report to the EC any DDs that could have led to a SADE, if required by the national regulations or by the EC,
- report to regulatory authorities any DDs that could have led to a SADE, as required by the national regulations, and
- supply the Sponsor, upon Sponsor's request, with any additional information related to the safety reporting of a particular event.

It should be noted that no documents should be submitted to any regulatory agency/ EC without approval by the Sponsor beforehand to assure accuracy and completeness of the information.

All DDs related to the identity, quality, durability, reliability, usability, safety or performance of an investigational device including the analysis of used or explanted investigational devices, where applicable, shall be documented throughout the registry study and managed by the Sponsor through internal SOPs.

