10 PATIENT DISCONTINUATION OF CONSENT FOR THE STUDY

IMPORTANT: This section is only applicable to sites and/or patients who have consented to have their data collected as part of this registry.

Patient participation in the registry study is considered complete when the EVD System is no longer required for drainage and monitoring of CSF. The registry study is considered complete upon the EVD System is no longer required for drainage and monitoring of CSF of the last patient.

A patient may withdraw consent for data to be collected in the registry study at any time during the registry study. The patient does not have to give a reason for withdrawal of consent. The investigator may exclude a patient if the patient or the patient's data does not fulfil the eligibility criteria (**Section 6.1-6.2**). The investigator may also decide to stop collecting a patient's data for the registry study if the investigator feels it is in the patient's best interest.

The Sponsor or its representative shall be notified immediately when a patient's consent is withdrawn or discontinued for any reason. Premature registry study end date and reason (if known) shall be documented on the CRF.

The data collected up to the date the patient has withdrawn consent will be included as part of the registry study results, as permitted by national laws and regulations. Additional safety information may be requested from a withdrawn or discontinued patient if it is considered clinically relevant.

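### The end of adverse-event collection is not defined relative to physical removal of the drain, so capture of removal hemorrhage is not assured and later events are not collected for completers

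*Protocol*

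**What the plan says.** Below, *end of need* stands for the moment at which, in the protocol's terms, the EVD System has ceased to be required.

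- **Adverse events (AEs).** Protocol 8.3 covers "all events that occurred between index procedure and until the EVD System is no longer required for drainage and monitoring of CSF". Section 9.6 covers "events that occurred from device implant until the subject exits the study", and 9.7 states that "AE and SAE recording will start at the point of device implant until the subject exits the study".
- **Exit.** Section 10: "Patient participation in the registry study is considered complete when the EVD System is no longer required for drainage and monitoring of CSF". The same section allows later safety information to be requested, but only from patients who withdrew or were discontinued.
- **Safety endpoint.** Section 3.6: "Device- or procedure-related adverse events (AEs) during the use of the device in the patient".
- **Device deficiencies.** Section 8.3 ends this review at end of need and refers the reader to 9.7.3, where review of a patient's "medical records will occur from the date of implant to the date of explant".
- **Events still open at exit.** Section 9.6: "If no resolution can be found in the medical record, the site will note it as ongoing".
- **SAP 8.10.1.** AEs are counted from enrollment to study termination or completion.
- **Background risk.** The synopsis names infection and hemorrhage as the most common complications. For a single-center pediatric population it gives hemorrhage of 10% at placement and reports "the incidence of hemorrhage on EVD removal to be 21.9" per cent. The adult range of 18 to 41% is not split by placement and removal.

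**The concern.** The registry's safety objective is to confirm continued safety, and its safety results are counts and percentages of events. Such counts can be interpreted only if every site closes the window at the same, known point. Here the closing point is a clinical state that the documents do not define: it could be the decision to stop draining, the last drainage, or the physical removal. The choice matters because the protocol's own background makes removal a source of hemorrhage, and because an infection such as ventriculitis or meningitis (listed in 9.4.1) may first show after the drain is out. If sites differ, reported rates depend partly on how a site read the text. Since 12.1.6 places source review after data collection for the last patient, differences between sites would come to light late.

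**Working it through.** **Step 1. The windows side by side.**

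| Place | Data | Opens | Closes |
|---|---|---|---|
| Protocol synopsis (Patient Duration), 6.3 | all registry data | implant / start of procedure | end of need |
| Protocol 8.3 | AEs and device deficiencies | index procedure | end of need |
| Protocol 9.6, 9.7 | AEs, SAEs | implant | study exit |
| Protocol 10 | patient completion | n/a | end of need |
| Protocol 9.7.3 | device deficiencies | implant | explant |
| Protocol 3.5 (indwelling days; non-infectious failure) | tertiary endpoints | implant | explant |
| SAP 8.10.1 | AEs | enrollment | study termination or completion |

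**Step 2. What follows.**

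- For completers, 9.6 and 9.7 add no time to 8.3, because section 10 puts completion at end of need.
- The same deficiency review has two stated end points (8.3 and 9.7.3).
- No section gives a completer AE follow-up after removal. An event first detected then is outside the window even if end of need is read as explant.
- A bleed during removal is inside the window if end of need means explant, and outside it if it means the earlier decision. The text does not settle which.
- The SAP opens its window at enrollment. Section 6.3 allows consent after end of need. If enrollment is taken as consent, the SAP window for those patients opens after the protocol's AE window has closed.
- Section 9.3 limits related procedures to those specific to the registry and treats complications of routine procedures not imposed by the plan as not related. Since all use is standard of care (2.3), a removal bleed that is recorded could still be classed as unrelated to the procedure.

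**Step 3. Size.** The denominator is the plan's own: 110 / (1 − 0.08) = 119.6, so 120 enrolled, as stated in 11.2. The 10% and 21.9% are cited literature rates and cannot be re-derived from the documents.

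- Ratio of removal to placement: 21.9 / 10 = 2.19.
- Removal share of the two, assuming no overlap: 21.9 / (10 + 21.9) = 21.9 / 31.9 = 68.7%.
- If the two were instead independent within a patient, the share of patients with any bleed whose only bleed is at removal would be (0.90 × 0.219) / (1 − 0.90 × 0.781) = 0.1971 / 0.2971 = 66.3%. The overlap assumption matters little.

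The share of children is not given, so it is varied here as an assumption. Expected counts are 120 × share × rate:

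| Assumed share of children | Children | Placement hemorrhages (10%) | Removal hemorrhages (21.9%) |
|---|---|---|---|
| 5% | 6 | 0.6 | 1.3 |
| 10% | 12 | 1.2 | 2.6 |
| 20% | 24 | 2.4 | 5.3 |
| 30% | 36 | 3.6 | 7.9 |
| 50% | 60 | 6.0 | 13.1 |

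The last column is the number at risk of being missed. The number actually missed lies between zero (every site collects to explant) and that figure (every site stops at an earlier decision). For adults, and for infection appearing after removal, the documents give no rate to work from.

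**The case against.** The best reply is that end of need and explant are one point in two wordings. Section 8.3 sends the reader to 9.7.3, which says explant. Inclusion criterion 3 asks patients whose system has already been removed for data up to end of need. The consent timings in 6.3 make no provision for a drain that is no longer needed but still in place. The safety endpoint speaks of use of the device in the patient, and a drain awaiting removal is still there. Removal dates are collected (8.2).

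This has force. A reader might infer from the literal wording of 8.3 that every removal hemorrhage falls outside the window, on the ground that need ends before the catheter is withdrawn. The documents do not support that: no section says that end of need precedes removal, and those just listed can be read the other way. A reader might also multiply 120 by 21.9% and conclude that about 26 hemorrhages would be lost. That requires all patients to be children and every removal bleed to go uncounted; neither is stated.

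It can also be said that safety has no formal test (SAP 8.10), no comparator and no performance goal, and that the length of follow-up after explant is a design choice. Both are true, and they limit the consequence. They do not answer two things: the end point is left to each site's reading, and on the kindest reading completers still have no AE collection after removal.

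**Conclusion.** The point holds as a defect of definition and coverage. Capture of hemorrhage at removal depends on the site and is not assured. Infection or hemorrhage first detected after removal is not collected for completers. Device deficiencies have conflicting end points, and the SAP window does not match the protocol's.

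On the single-center pediatric figures, removal accounts for about 69% of placement-plus-removal hemorrhages if the two do not overlap. At an assumed 5% to 50% children among 120 patients, about 1.3 to 13.1 removal hemorrhages are at risk, and none if sites collect to explant. The adult loss and the post-removal infection loss cannot be quantified from the documents.

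The consequence is possible under-counting in the descriptive safety results. The primary endpoint test against the 80% goal is not affected.

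**What to change.** 1. Reconcile the synopsis, protocol 6.3, 8.3, 9.6, 9.7, 9.7.3 and 10, and SAP 8.10.1, to one end point for AEs and device deficiencies, stated relative to explant. It should at minimum include the removal procedure and extend to a point after it chosen by the sponsor, using the existing medical record. Avoid a rule that closes at the earlier of two dates, since it could shut before late events appear.
2. State in 9.3 that removal of the device counts as a related procedure when relatedness is assessed.
3. Start the SAP's AE window at implant, as the protocol does.
4. Tabulate events by phase: insertion, indwelling, and removal or after removal.
5. Leave the primary endpoint's own end point unchanged.

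The cost is a protocol amendment, SAP wording and somewhat more chart review per patient. Removal dates are already collected, and 8.2 already asks whether a permanent shunt was required after end of need, so sites already look past that point for performance data. No visits, procedures or extra patients are needed. Reported AE rates may rise.
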